11.6. Inclusion in Analysis

All data available from all participants will be used for the analyses. If a child has become hypoglycaemic (BG $< 4.0 \text{ mmol/l}$) during the profile period then subsequent data will be analysed separately. If any child has had to treat a high BG level with additional insulin (except for a correction dose at the evening meal), then subsequent profile data will be analysed separately. However in either instance, the data up to the event will be included in all analyses. The two other meals would still be eligible for the study analyses if there were no similar events.

If there have been any protocol breaches, such as further food during the evening after the main meal, then all the subsequent data will not be used in the analysis for that meal. Education of the participants and parents will be vital to ensure that such eventualities are rare.

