5. OBJECTIVES AND OUTCOME MEASURES

Objectives	Outcome Measures	Timepoint(s) of evaluation of this outcome measure (if applicable)

Primary Objective To determine whether additional insulin boluses for the fat and protein content of a meal given before, one or two hours after a meal optimise post-prandial blood glucose levels in children with Type 1 diabetes using multiple daily
	
Continuous subcutaneous glucose profiles will be examined to determine –
 
 mean post-prandial glucose excursion for 8 hours following the test meal 	
Continuous Glucose Monitoring profiles during the 12 hours following the test meals

[figure not shown]
injections?		

Secondary Objectives
 
To examine other indices of BG control following additional insulin boluses for the fat and protein content of a meal given before, one or two hours after a meal in children with Type 1 diabetes using multiple daily injections?
	
Continuous subcutaneous glucose profiles will be examined to determine –
 
 • peak BG level • peak BG excursion from baseline (pre-meal BG level) • time of peak BG level • timing of peak BG excursion 
area under the curve at time-points 0-3 hours, 3-5 hours, 5-8 hours, 8-12 hours post-meal
	
Continuous Glucose Monitoring profiles during the 12 hours following the test meals

Tertiary Objectives
 
1. To assess the acceptability of giving additional insulin doses for fat and protein to children using MDI
 
2. To assess the safety of giving additional insulin doses for fat and protein to children using MDI
	
1. Questionnaires to parents and children during and at the end of the study
 
2. All episodes of hypoglycaemia (BG less than 4 mmol/l) or hyperglycaemia (BG >12 mmol/l) either on CGM or self-monitoring of BG
	
Collection of data during and at the end of the study

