11.1. Description of Statistical Methods

Descriptive statistics will be used to describe the group demographics and outcomes.

The continuous glucose records will be analysed methodically by the CI, research dietitian and statistician. Data to be obtained include –

- pre-meal BG level
- peak BG level
- peak BG excursion from baseline at 3, 5, 8 and 12 hours following the meal
- time of peak BG level
- time of peak BG excursion
- area under the curve at time-points 0-4 hours, 4-6 hours, 6-8 hours, 8-12 hours post-meal

The relationship between the insulin timing and the mean change in postprandial blood glucose levels will be analysed and described.

Comparisons using paired t tests for normally distributed data, and Mann-Whitney U tests for non-parametric data will be used to examine the differences in areas under the postprandial BG curves and the postprandial BG levels by insulin timing.

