11.4. Criteria for the Termination of the Trial

We would only anticipate 10 episodes of severe hypoglycaemia in 340 patients per year. Therefore the likelihood of a severe hypo occurring during this study under normal circumstances would be very small. So if we assume there is no increase in risk then we would only expect to see 2 severe hypos in one of the two arms in 3 out of every 10,000 trials, for a single hypo in either arm this increases to about 1 in every 100 trials. Therefore we would terminate the trial if we had 2 severe hypos occurring on any arm of the trial.

11.5. Procedure for Accounting for Missing, Unused, and Spurious Data.

We will use boxplots to identify outlying, unusual or spurious data using pre-defined decision rules (e.g. upper or lower quartiles $\pm 1.5 \times \text{IQR}$). In the case of implausible or unlikely outcome data we will look back at CRF's to rule out data handling errors. If outliers cannot be resolved then we will exclude this particular result from the main analysis. We intend to use a complete case analysis but we will conduct a sensitivity analysis to assess the impact of any missing data using appropriate multiple imputation methods.

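### The outlier rule can drop genuine extremes from the main analysis, and the 8-hour primary mean is undefined for a trace cut at a low or a treated high

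*Combined protocol and SAP*

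**What the plan says.** The primary outcome (Synopsis and Section 5) is the "mean post-prandial glucose excursion for 8 hours following the test meal".

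Section 11.6 covers interrupted traces. If a child's BG falls below 4.0 mmol/l "during the profile period then subsequent data will be analysed separately", and the same applies after insulin given for a later high. For both: "However in either instance, the data up to the event will be included in all analyses". After a protocol breach such as food later in the evening, "then all the subsequent data will not be used in the analysis for that meal". Section 6.3 adds that a low before a due second study dose leads to that dose being omitted, and that such data are analysed separately.

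Section 11.5 covers missing and outlying values. On missing data: "We intend to use a complete case analysis", with multiple imputation as a sensitivity analysis. Outliers are flagged by boxplot, with quartiles ± 1.5 x IQR given as an example. For implausible or unlikely values, "we will look back at CRF's to rule out data handling errors", and then: "If outliers cannot be resolved then we will exclude this particular result from the main analysis".

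Section 11.1 names the tests: "Comparisons using paired t tests for normally distributed data, and Mann-Whitney U tests for non-parametric data will be used".

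**The concern.** Both rules decide what enters the primary comparison according to glucose observed after dosing.

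**Outliers.** The look-back searches for handling errors. A true extreme excursion has none to find, and the plan does not define when an outlier counts as resolved. Section 6.3 has the outcomes calculated from the sensor download, whereas Section 12.1 has CRF data obtained from diaries, so a CRF check may be unable to confirm a correct sensor value. Deleting true extremes understates the variance, and the paired t test then rejects too often. No analysis with the excluded values kept is planned.

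**Cut traces.** No section says how an 8-hour mean is formed from a trace that stops early. Two analysts following the text could report different primary results from the same data. The retained window is also set by an event that insulin timing may influence.

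**Working it through.** **1. The plan's own figure.** Section 11.2 gives 36 children for 80% power to detect 2 mmol/L at the 5% level. No SD is stated, so 36 can be neither reproduced nor refuted. Back-solving for a two-sided paired comparison gives an SD of differences of 2 x √36 / (1.960 + 0.842) = 4.28 mmol/L, or 4.16 with the noncentral t. That statement concerns the 5-hour mean; using 4.16 for the 8-hour mean below is an assumption.

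**2. Outlier fence.** For a normal population the upper fence lies at 0.674 + 1.5 x 1.349 = 2.70 SD, so 0.70% of error-free values fall outside the two fences. In samples of 40 the quartiles are estimated and about 1.5% are flagged, or 1.8 of 120 meals. At least one meal is flagged in 69-75% of trials when the fence is drawn per timing.

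Type I error was simulated with 40,000 trials per setting, 40 children, three timings, normal data, no true difference, and a two-sided paired t test on one pair of timings. The Monte Carlo SE is 0.11-0.13 percentage points. The columns give the assumed between-timing correlation.

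| Fence | 0 | 0.25 | 0.5 | 0.75 |
|---|---|---|---|---|
| None | 5.0% | 4.9% | 5.1% | 5.1% |
| Per timing, all flagged deleted | 7.4% | 6.7% | 6.2% | 5.6% |
| Per timing, half of flagged kept | 6.1% | 5.7% | 5.6% | 5.3% |
| On paired differences, all deleted | 7.7% | 7.7% | 7.9% | 7.8% |
| On paired differences, half kept | 6.2% | 6.2% | 6.3% | 6.2% |
| Pooled meals, all deleted | 5.1% | 4.9% | 5.0% | 5.1% |

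Repeat runs on the difference scale span 7.5-8.0%. For skewed data the plan turns to the Mann-Whitney test and the result depends on the correlation, so no figure is given.

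**3. Cut trace, shortened-window reading.** If the trace is cut at t hours and the mean to the cut is entered, then

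entered value − full 8-hour mean = (8 − t)/8 x (mean before − mean after).

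Illustrations with assumed profiles (mmol/L):

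- +1 to 2.5 h, then −2: full mean (2.5 x 1 + 5.5 x (−2))/8 = −1.06; entered as +1.00.
- +1 to 6 h, then −2: full mean (6 x 1 + 2 x (−2))/8 = +0.25; entered as +1.00.
- 0 to 2.5 h, then +3: full mean (2.5 x 0 + 5.5 x 3)/8 = +2.06; entered as 0.

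The sign is not fixed. These are shifts in one meal. The shift in a timing's mean is diluted by the share of meals cut, and it cancels from the comparison if profile shape and the time of events do not differ by timing.

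**4. Cut trace, complete-case reading.** If a cut meal counts as missing and each meal is cut independently with assumed probability p, 40 x (1 − p)² children remain for one pair of timings. For p = 5%, 10%, 20% and 30% this is 36.1, 32.4, 25.6 and 19.6. With the back-solved SD of 4.16, power is 84% at 40, 80% at 36, 75% at 32 and 53% at 20. A 5% rate would already use up the margin between 40 and 36. The documents give no rate of BG below 4.0 mmol/l.

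**The case against.** **The cut-trace text can be read coherently.** The plan has AUC windows as well as the 8-hour mean. Data up to the event could serve the windows that end before it, while the 8-hour mean is treated as missing and checked by imputation. This is sensible, but the text keeps the early data in all analyses, which literally includes the primary, and no section says that a cut trace counts as missing. The gap stands.

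**Setting post-event glucose aside is deliberate.** Rescue carbohydrate or corrective insulin changes the profile, and a full-trace mean can make a meal with a low look favourable. This objection stands. A reader might infer that the full trace must be the main analysis, but the documents do not support that. They support only the need to state one rule.

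**The CRF check offers some protection.** Finger-prick values before meals, at bedtime and on waking (Section 6.3) can expose entry errors and confirm some extremes. They cannot confirm overnight values between finger-pricks, and the text still does not limit exclusion to errors.

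**The inflation is modest and conditional.** The fence is only an example, and the plan does not say whether it applies per timing, to pooled meals or to differences. This stands and is carried into the verdict.

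**Conclusion.** Both points hold and should be fixed before analysis.

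The outlier rule is stated and can remove genuine extremes. Its cost is a paired-t type I error of about 5.6-7.4% (fence per timing) or 7.5-8% (fence on differences) in place of 5%. This rests on normal data, 40 children, the example fence and deletion of every flagged value. It is an upper case: with half of the flagged values kept it is 5.3-6.3%, and with a pooled fence there is no inflation. A reader might infer that the trial would run at 8%. The documents do not support this, because they fix neither the fence, its scale nor the share of flagged values that would be resolved.

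The primary value for a cut trace is undefined: it is either a mean over an outcome-dependent window or missing. A reader might infer that one timing is favoured. That cannot be shown, because the documents give no profile, no SD and no rate of lows by timing. Confidence is high that the definition is missing, but the size and sign of its effect are unknown.

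**What to change.** **Outliers (Section 11.5).** In the main analysis exclude only values with a verified recording or sensor error, judged without regard to insulin timing. Fix the fence and the scale on which it is drawn, and report the fence-excluded result as a sensitivity analysis.

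**Cut traces (Section 11.6).** Do not enter a mean over a shortened window as the 8-hour primary value. State one rule for the main analysis:

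- the full recorded CGM trace, by randomised timing; or
- post-event glucose set aside, with the remaining hours treated as missing and imputed.

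Run the other as sensitivity, and report episodes of BG below 4.0 mmol/l by timing beside the primary result. Apply the same rule to meals cut by a food breach and to meals with an omitted second dose.

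**Cost.** This needs an amendment to Section 11, which under Appendix B goes to the sponsor before the REC or MHRA, and a little more analysis. No new data are needed: CGM records every 5 minutes and hypoglycaemia is already a tertiary outcome. Under the full-trace option post-rescue glucose enters the mean, so lows by timing must be read with it.

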2. SYNOPSIS

Trial Title	Investigation of Appropriate Timing of Additional Insulin Dosing for Fat and Protein in Children with Type 1 Diabetes using Multiple Daily Injections	
Internal ref. no. (or short title)	Fat/Protein Study	
Clinical Phase	Phase 4	
Trial Design	Controlled observational study	
Trial Participants	Children aged 6 to under 18 years of age with type 1 diabetes (T1DM)	
Planned Sample Size	40	
Treatment duration	1 week	
Follow up duration	No follow-up at the end of the trial period	
Planned Trial Period	1 year	
	Objectives	Outcome Measures
Primary	To determine whether additional insulin boluses for the fat and protein content of a meal given before, one or two hours after a meal optimise post-prandial blood glucose levels in children with Type 1 diabetes using multiple daily injections?	Continuous subcutaneous glucose profiles will be examined to determine – 
 • mean post-prandial glucose excursion for 8 hours following the test meal
Secondary	To examine other indices of BG control following additional insulin boluses for the fat and protein content of a meal given before, one or two hours after a meal in children with Type 1 diabetes using multiple daily injections?	Continuous subcutaneous glucose profiles will be examined to determine – 
 • peak BG level • peak BG excursion from baseline (pre-meal BG level) • time of peak BG level from baseline measurement • Rate of BG excursion from baseline to peak • mean post-prandial glucose excursion for 5 and 12 hours following the test meal • area under the curve at time-points 0-3 hours, 3-5 hours, 5-8 hours, 8-12 hours post-meal • Time from baseline BG at which BG returns to baseline level
Investigational Medicinal Product(s)	Insulin	
Formulation, Dose, Route of Administration	Insulin Aspart (NovoRapid) given in a dose according to the protocol, subcutaneously	

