Participants will be asked not to give a correction dose before the meal if the BG level is between 7-12mmol/l as this would interfere with the analysis. They will be asked, if possible, not to carry out the test meals if their pre-meal BG is greater than 12 mmol/l. But if they have to do the test meal with a high pre-meal BG (above 12 mmol/l) they will be instructed to give their usual correction bolus in addition to the prescribed insulin dose for the test meal. This data will be analysed separately. If BG is below 4mmol/l (hypoglycaemic) or above 16mmol/l participants will be asked to abandon the study evening and repeat on another evening. Full written instructions will be provided to the family for all aspects of the insulin dosing for the study meals.

During the study on the standardised meal days children will be instructed not to eat any food after the meal during the evening, and not to correct any later BG levels unless they are dangerously high (BG over 16 mmol/l with ketones over 0.5 mmol/l). If BG levels go low at any time (BG less than 4 mmol/l) children will be instructed to treat the hypoglycaemia according to their usual management, and omit

any further study doses of insulin if the hypoglycaemia occurs after a first study dose and a second is due. This data will be analysed separately. Children and families will be asked to complete diaries during the trial week.

At the end of the study period (the day after the third meal), children will come back to the research facility or clinic for the end of study visit (visit 3). A research nurse or dietitian will remove the CGM sensor and download the data onto a secure laptop. Children and their families will then be asked to complete a short questionnaire about the acceptability of using the extra insulin doses, and their perceptions as to whether there were any beneficial or adverse effects.

The study dietitian will calculate standard outcomes from each patient's sensor download and pass on anonymously to the study statistician to analyse the data.

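### Section 11.6 lets a profile stopped before its peak supply the maximum of a stub as its peak BG, peak excursion and time of peak; separately, the synopsis rate-to-peak outcome has no value when BG never rises

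*Combined protocol and SAP*

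**What the plan says.** Peak outcomes appear in three places. The Synopsis lists peak BG, peak excursion from baseline, "time of peak BG level from baseline measurement" and "Rate of BG excursion from baseline to peak" as secondary outcomes. The Section 5 table lists peak BG, peak excursion, time of peak BG and "timing of peak BG excursion", but no rate. Section 11.1 lists peak BG, peak excursion at 3, 5, 8 and 12 hours, time of peak BG and "time of peak BG excursion", again with no rate. Evaluation runs over the 12 hours after the meal (Section 5), with a reading every 5 minutes (Section 6.3).

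Under Section 11.6, if BG falls below 4.0 mmol/l "during the profile period then subsequent data will be analysed separately". The same applies after extra insulin for a high, other than a correction at the meal itself. The part before the event is kept: "However in either instance, the data up to the event will be included in all analyses".

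Section 11.5 says "We intend to use a complete case analysis", with multiple imputation as a sensitivity analysis. It does not say whether a stopped profile, or a rate that cannot be calculated, counts as missing. No section gives a search window for time of peak, a minimum observation time, a formula for the rate, or a rule for a profile that does not rise.

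**The concern.** A maximum and its timing describe a whole profile. They cannot be read from its first part unless the peak is known to have occurred already. Stopping a trace at a low is reasonable, because what follows reflects treatment of the low. Passing the remainder into every analysis is not reasonable for these outcomes. If BG dips early and the fat and protein effect arrives later, the stub returns an early, small peak. That number is finite and plausible, so neither the missing-data rule nor the boxplot screen in Section 11.5 need catch it. It would then be compared with a 12-hour peak from the same child on another evening.

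The trial compares insulin timings, so when glucose peaks is close to its scientific question. If profiles are stopped early to different extents on the three evenings, part of any observed difference in peak timing comes from the scoring rule.

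The rate outcome has its own gap. The natural reading is rise divided by time to peak, and where BG never exceeds the pre-meal value both are zero. Such profiles are possible because a raised start may go uncorrected: "Participants will be asked not to give a correction dose before the meal if the BG level is between 7-12mmol/l".

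**Working it through.** **The plan's own figure.** The only design figure is 36 children for 80% power to detect 2 mmol/L in mean 5-hour excursion (Section 11.2). No SD is stated. Solving the normal-approximation paired formula at two-sided 5% gives an SD of the difference of 2 × √36 / (1.960 + 0.842) = 4.28 mmol/L. The figure can be neither confirmed nor refuted, and it does not concern peak outcomes.

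**What a stop does to one profile.** The curves below are assumed, drawn on a 5-minute grid over 12 hours and stopped at the first BG below 4.0. Rate = (peak − baseline) / time of peak.

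| Assumed profile | First low | Full: time of peak, excursion, rate | Stopped: time of peak, excursion, rate |
|---|---|---|---|
| A. Falls, then late rise | 60 min | 360 min, 4.43, 4.43/6 = 0.74 per h | 0 min, 0, 0/0 |
| B. Small early rise, low, late rise | 75 min | 360 min, 3.61, 3.61/6 = 0.60 per h | 20 min, 1.07, 1.07/(20/60) = 3.2 per h |
| C. Early peak, later low | 200 min | 60 min, 3.72, 3.72 per h | unchanged |
| D. Steady fall to a low | 410 min | 0 min, 0, 0/0 | unchanged |
| E. Steady fall, no low | none | 0 min, 0, 0/0 | not stopped |

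A and B show the error. C shows that a stop after the peak does no harm. D and E show that the 0/0 rate arises without Section 11.6. In D and E the time of peak has a value, 0 minutes, which is degenerate but not undefined.

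**What it does to a comparison.** Let p be the share of profiles stopped before the peak, T the mean true time of peak (taken as the same in stopped and unstopped profiles) and s the time recorded from a stub. The recorded mean is (1 − p)T + ps. With c for control, d for a delayed timing and D = T_d − T_c, the recorded difference, delayed minus control, is

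(1 − p_d)D + (p_c − p_d)(T_c − s).

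With equal shares the second term vanishes and a true difference D shrinks to (1 − p)D. With no true difference, and assuming T = 300 and s = 20 minutes, the false difference is 280 × (p_c − p_d):

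| p_c | p_d | False difference (min) |
|---|---|---|
| 30% | 10% | +56 |
| 20% | 10% | +28 |
| 10% | 10% | 0 |
| 10% | 20% | −28 |

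The documents supply neither share. Section 11.4 gives only a background rate of severe hypoglycaemia, 10 episodes in 340 patients per year, which is not a rate of BG below 4.0 and is not split by timing.

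**The case against.** Separating the data after a low is sound. Section 6.3 has the low treated and any pending second study dose omitted, so the later maximum is not a clean response to the tested timing. This stands. It also means that the full-profile values above describe a hypothetical evening without rescue, and that comparing stopped with untreated traces cannot measure the bias in this trial. It does not make the stub's maximum a peak.

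It can also be said that Section 11.5 might treat a stopped profile as incomplete and set it aside, so that the text is ambiguous and not wrong. But Section 11.6 is explicit that the earlier data enter every analysis, and nothing in 11.5 overrides it. Section 11.1 does tie peak excursion to four horizons, which helps at horizons reached before the stop. It does not say that later horizons go unscored, and peak BG and time of peak have no horizon.

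A reader might infer that wrong values arise most often on the control evening and that the timing difference is therefore biased toward zero. The first part is plausible for early events: until 60 minutes the control evening carries the carbohydrate and the fat/protein dose, and the delayed evenings carry only the carbohydrate dose. It remains an inference. No lows by timing are given, delayed doses could cause later lows within the 12 hours, and the table shows that the sign depends on the shares.

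**Conclusion.** The point holds for peak BG, peak excursion and time of peak. As written, Section 11.6 gives a wrong value for any profile stopped before its peak and a right one for any stopped after it. In a single assumed profile the error in time of peak reaches 340 to 360 minutes. Between timings, neither size nor direction can be computed; the minutes given for the comparison are illustrations resting on assumed shares and peak times.

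The 0/0 rate is a separate gap in the definition of an outcome found only in the Synopsis, and should not be charged to Section 11.6. All the affected outcomes are secondary, and this point does not address the primary 8-hour mean excursion. The wording should still be changed before analysis, because the wrong values would not be visible in the results and the correction needs no new data.

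**What to change.** 1. In Section 11.6, exempt peak BG, peak excursion and time of peak from the rule on data up to the event. State that the maximum of a stopped profile is not taken as its peak.
2. Score these outcomes in pre-set windows, only where the window is fully observed. Use one set of intervals running to 12 hours in the Synopsis, Section 5 and Section 11.1. At present the area-under-curve intervals are 0-3, 3-5, 5-8 and 8-12 hours in the first two and 0-4, 4-6, 6-8 and 8-12 hours in the third.
3. Treat a window stopped by a low or by rescue insulin as missing. For these outcomes make the multiple imputation of Section 11.5 the main analysis and complete case the sensitivity analysis. Otherwise the main comparison is limited to profiles without a low, which selects on the result. State that the imputed value stands for an evening without rescue.
4. Replace rate-to-peak with change from pre-meal BG at fixed early times, for example 1 and 2 hours. It is negative when BG falls, so a profile that does not rise still has a value. Handle profiles stopped before that time as in step 3.
5. Report by timing the number of profiles stopped before each window ends and the number that never rise above pre-meal BG.

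The cost is wording in the Synopsis and Sections 5, 11.1, 11.5 and 11.6. Time of peak and rate-to-peak are redefined, and late-window results rest partly on imputation and are less precise.
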